#### 4.6 Other analyses

The following data will be summarised descriptively, by randomised group and overall:

A	B	C
	Objective	Endpoints to display
1	Assess mortality rate during index hospitalisation, in-hospital and at 90 days	a) In-hospital mortality (index admission) and b) 90-day mortality
2	Assess the ability to deliver the trial including the time to first dose, data completeness and participant withdrawal	Data completeness (%)
3	Assess the total volume of intravenous fluid in each arm at 6 hours and 24 hours	Volume of randomised fluid delivered in each arm a) in the first 6hrs and b) more than 6hrs to 24hrs
4	Assess the level of critical care interventions administered	Proportion of participants needing critical care intervention: a) Intravenous vasopressors, b) renal replacement therapy and c) invasive ventilation
5	Investigate the length of hospital stay including critical care (HDU/ICU) admission	a) Proportion of patients admitted to critical care (HDU/ICU) b) Length of stay in critical care (HDU/ICU) c) Length of hospital stay
6	Investigate the proportion of patients readmitted to hospital in first 90 days after discharge	Proportion of patients readmitted in first 90 days after discharge

A	B	C
7	Delineate the proportion of patients developing any complications including acute kidney injury, pulmonary oedema and allergy including severe allergic reactions	Proportion of patients developing each, or any, of: a) acute kidney injury (as defined by NICE https://cks.nice.org.uk/acute-kidney-injury#!scenario ); b) pulmonary oedema (radiology diagnosis or requirement for rescue management (new diuretic use)); and c) allergy or anaphylaxis (requirement for rescue management (antihistamines, adrenaline, intravenous fluids, steroids))
For the economist		
8	To assess patient quality of life measures using EQ-5D-5L questionnaire	Health Related Quality of life (EQ-5D-5L) for the first 50 patients randomised (see section 4.8) a) at baseline b) at 7 days and c) at 180 days
9	To assess secondary care costs at 30 days	Service use at 30 days: a) number of readmissions, and b) length of stay at ward level and in critical care (HDU/ICU)

In addition, the following exploratory analyses will be considered. If deemed inappropriate based on available data, where feasible, suitable alternatives will be used:

- a) If the data permits, the effect of compliance (what cumulative dose of novel intervention or standard care was received) on intervention effect will be explored using a complier average causal effects approach. Descriptive analysis of changes in compliance over time in small and large sites may also be considered.
- b) Other continuous outcomes (e.g. volume of intravenous fluid, length of stay) will be analysed using mixed effects linear models, while the other outcomes involving proportions (e.g. proportion receiving renal replacement therapy, vasopressor infusion, invasive ventilation, readmissions within 90 days) will be analysed as per the main clinical outcome (with a mixed effects logistic regression). Site will be included as the random effect.
- c) The intervention effect on proportion admitted to critical care (HDU or ICU) will be analysed using mixed effects logistic regression as per the main clinical outcome.
- d) The observed patterns of any missing data will be reported by randomised group, across the range of outcomes measured and, where appropriate, by time of measurement. This will inform the missing data handling strategies to be taken forward in the subsequent confirmatory trial.

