#### **2.1.2 Secondary Objectives**

1. To assess the mortality rate during index hospitalisation, in-hospital and at 90 days;
2. To assess the ability to deliver the trial including the time to first dose, data completeness and participant withdrawal;
3. To quantify the proportion of patients who receive any other fluid apart, from the one being studied, in the first 6 hours after recruitment;
4. To assess the total volume of intravenous fluid in each arm at 6 hours and 24 hours
5. To assess the level of critical care interventions administered;
6. To investigate the length of hospital stay including critical care (HDU/ICU) admission;
7. To investigate the proportion of patients readmitted to hospital in first 90 days after discharge;
8. Delineate the proportion of patients developing any complications including acute kidney injury, pulmonary oedema and allergy including severe allergic reactions;
9. To assess patient quality of life measures using EQ-5D-5L questionnaire;
10. To assess secondary care costs at 30 days.

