#### **2.2.2 Secondary Endpoints**

[figure not shown]
1. In-hospital mortality and 90-day mortality;
2. Time to start of IMP;
3. Data completeness;
4. Study withdrawal;
5. Volume of randomised fluid delivered in each arm in the first 6hrs and 24hrs;
6. Proportion of participants needing critical care intervention: Intravenous vasopressors, renal replacement therapy and invasive ventilation;

7. Proportion of patients who receive any other fluid apart from intervention or control in first 6 hrs after recruitment;
8. Proportion of patients admitted to critical care (HDU/ICU); length of stay in critical care (HDU/ICU);
9. Length of hospital stay;
10. Proportion of patients readmitted in first 90 days after discharge;
11. Proportion of patients developing any of: acute kidney injury (Defined by NICE (<https://cks.nice.org.uk/acute-kidney-injury#!scenario>); pulmonary oedema (Radiology diagnosis or requirement for rescue management (new diuretic use); and allergy or anaphylaxis (Requirement for rescue management (antihistamines, adrenaline, intravenous fluids, steroids));
12. Health Related Quality of life (EQ-5D-5L) at 7 and 180 days for the first 50 patients;
13. Secondary care costs at 30 days (calculated from readmissions and length of stay at ward level and in critical care (HDU/ICU).

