### **3. STUDY DESIGN**

This trial will be an open label two-arm, multicentre, pragmatic, parallel group randomised trial of adult patients with community acquired sepsis recruited from the Emergency Department and Medical and Surgical Assessment Units across ~15 UK NHS Hospitals. The treatment phase will be the first 6 hours following randomisation. 30-day and 90-day follow up will be conducted using routine data only. The exception to this will be the first 50 patients enrolled in the study, Health Related Quality of Life (HRQoL) will be measured using the EQ-5D-5L at baseline, 7 days and at 180 days. At baseline, the participant or their relative will be asked to recall the quality of life 4 weeks prior to the index hospital admission (modified EQ-5D-5L). Questionnaires will be administered by direct participant/relative completion or postal survey with telephone follow up for non-responders after two mailings two weeks apart.

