### **6.3 DOSING REGIME**

Participants allocated to the treatment arm will receive intravenous 5% Human Albumin Solution (HAS) administered as the sole intravenous resuscitation fluid during the initial 6-hour resuscitation period. It is anticipated that most participants will receive approximately 10ml/kg in the first 3 hours using 250-500ml rapid infusion (bolus) of HAS for resuscitation based on clinical judgement, using clinical assessment supplemented by technology within the usual scope of practice. After 3 hours, further HAS boluses for resuscitation up to 6 hours post-randomisation will be at clinical discretion and will be documented in the eCRF. Both vital signs and lactate, if measured, prior to treatment starting and at 1,3,5,7 hours (+/-30mins) after randomisation, will be recorded in the eCRF as well as source data worksheets or medical notes.

To avoid contamination, participants in the HAS arm should not receive balanced crystalloid or other fluid as a resuscitation fluid in the first 6 hours post randomisation. If the treating clinician believes resuscitation to euvolaemia has been completed within the 6hour period post randomisation and wishes to commence slow maintenance fluid within this timeframe using balanced crystalloid, this should be at a rate of no more than 125ml/hour. The reason for the fluid should be clearly recorded in the eCRF i.e., maintenance rather than resuscitation. In the subsequent event of further clinical deterioration during the intervention timeframe requiring resuscitation fluid, further boluses of HAS should be administered and documented as further bolus fluid for resuscitation.

Participants allocated to the usual care arm will receive intravenous balanced crystalloid administered as the sole intravenous fluid during the initial 6 hour resuscitation period post randomisation. It is anticipated that most participants will receive approximately 30ml/kg in the first 3 hours using 250-1000ml rapid infusion (bolus) of balanced crystalloid for fluid resuscitation based on clinical judgement, using clinical assessment supplemented by technology within the usual scope of practice. Thereafter, further crystalloid boluses for resuscitation up to 6 hours will be at the discretion of the clinical team and will be documented in the eCRF. Both vital signs and lactate, if measured, prior to treatment starting and at 1,3,5,7 hours (+/-30mins), will be recorded in the eCRF as well as source data or medical notes.

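### The fluid-volume objective asks for total IV fluid, but its endpoint counts only randomised fluid, which is not a like-for-like comparison between arms after hour 6

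*SAP*

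**What the plan says.** The objective and the endpoint use different quantities in both documents.

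- Protocol 2.1.2, objective 4: "To assess the total volume of intravenous fluid in each arm at 6 hours and 24 hours".
- Protocol 2.2.2, endpoint 5: "Volume of randomised fluid delivered in each arm in the first 6hrs and 24hrs".
- SAP 4.6, row 3, objective column: "Assess the total volume of intravenous fluid in each arm at 6 hours and 24 hours".
- SAP 4.6, row 3, endpoint column: "Volume of randomised fluid delivered in each arm a) in the first 6hrs and b) more than 6hrs to 24hrs".

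The SAP thus carries over the protocol's move from total to randomised fluid, and replaces the 24-hour window with one that starts at 6 hours. Neither document defines randomised fluid or says whether maintenance fluid belongs to it.

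Protocol section 3 sets the intervention period: "The treatment phase will be the first 6 hours following randomisation". Within it, Protocol 6.3 allows for a clinician in the albumin (HAS) arm who "wishes to commence slow maintenance fluid within this timeframe using balanced crystalloid" and adds that "this should be at a rate of no more than 125ml/hour". The same ceiling applies to maintenance in the control arm, where balanced crystalloid is to be "administered as the sole intravenous fluid during the initial 6 hour resuscitation period post randomisation".

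SAP 4.3 has related outputs: distribution plots of allocated resuscitation fluid for several windows including 0-24 hours, the volume of crossover fluid to 6 and to 24 hours, and the proportion of patients given any non-study fluid in the first 6 hours. SAP 4.6(b) lists IV fluid volume as an example of an outcome for a mixed linear model, without saying which fluid or which window.

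**The concern.** Protocol 1.2 argues that a colloid should achieve a given physiological effect with less volume, and cites a 3:1 ratio. Testing that idea, or planning fluid exposure in a definitive trial, needs all the IV fluid each patient received. A count limited to the allocated product measures delivery of the allocation instead.

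The two quantities diverge unequally by arm. The comparator is also the usual-care fluid, and nothing in the protocol requires albumin after hour 6. Ordinary later care with balanced crystalloid therefore adds to the control arm's total and adds nothing to the albumin arm's. A reader of the row 3 table could take the resulting gap as a difference in fluid requirement.

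**Working it through.** The plan states no expected value, SD or precision for this endpoint, so there is no figure to reproduce. The check compares the definitions and then sizes the gap.

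**Inputs from Protocol 6.3 and section 3.** About 10 mL/kg (HAS) and 30 mL/kg (crystalloid) are anticipated in the first 3 hours; maintenance is capped at 125 mL/h in the first 6 hours; treatment lasts 6 hours.

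**Assumptions.** Weight is 70 kg (range 50 to 100), with no resuscitation fluid beyond the anticipated volumes. Maintenance is balanced crystalloid and equal in both arms. After 6 hours both arms receive balanced crystalloid at the same 0 to 125 mL/h. The documents give no rate after 6 hours, so the cap is carried forward only to bound the illustration.

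**Step 1: is total IV fluid reported anywhere?** Row 3 gives allocated fluid. SAP 4.3 gives crossover volume separately and does not add it to allocated volume within patients. Non-study fluid appears as a proportion for 0-6 hours only, with no volume and nothing later. No listed output is total IV fluid by arm at 6 or 24 hours.

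**Step 2: the >6-24 hour window.** Upper bound: 125 mL/h × 18 h = 2,250 mL per patient.

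- Randomised fluid: crystalloid arm 0 to 2,250 mL, HAS arm 0 mL; difference 0 to 2,250 mL.
- Total fluid: the same in both arms; difference 0 mL.

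If randomised fluid means resuscitation fluid only, later maintenance drops out of both arms. A crystalloid bolus at hour 8 would still count in one arm and not in the other.

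**Step 3: the 0-6 hour window.** Ceiling: 125 mL/h × 6 h = 750 mL. Maintenance in hours 3-6 only: 125 × 3 = 375 mL. At 70 kg the resuscitation volumes are 10 × 70 = 700 mL and 30 × 70 = 2,100 mL.

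| 0-6 h, 375 mL maintenance in both arms | HAS | Crystalloid | Difference |
|---|---|---|---|
| Randomised fluid, maintenance counted | 700 | 2,475 | 1,775 |
| Total fluid | 1,075 | 2,475 | 1,400 |

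The excess is 375 mL, and 375/1,775 = 21% of the apparent difference. At the 750 mL ceiling the share is 750/2,150 = 35% at 70 kg, 750/1,750 = 43% at 50 kg and 750/2,750 = 27% at 100 kg. On a resuscitation-only definition the excess is 0.

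**Step 4: 0-24 hours, the protocol's window, at the upper bound after 6 hours.** Randomised fluid: (2,475 + 2,250) − 700 = 4,025 mL. Total fluid: (2,475 + 2,250) − (1,075 + 2,250) = 1,400 mL. The excess of 2,625 mL is 375 + 2,250 and does not depend on weight.

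**Step 5: does splitting at 6 hours lose the 24-hour result?** In complete cases the two window means add exactly to the 0-24 hour mean. Medians and SDs do not add. With assumed log-normal volumes (log-means 7 and 6.5, log-SDs 0.6 and 1.0, log-scale correlation −0.5 to 0.5), the summed medians were about 1,765 mL against a true median of 1,890 to 2,088 mL. The true SD was 1,432 to 1,957 mL, against about 1,670 mL if the windows are treated as independent. SAP 4.3 plots allocated resuscitation fluid for 0-24 hours, so for that quantity the median can be read off. The split is a minor point.

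**The case against.** The strongest reply is that SAP 4.3 already supplies most of what is missing. Balanced crystalloid given to an albumin patient would ordinarily appear as crossover volume, reported to 6 and to 24 hours, and allocated plus crossover volume within a patient gives all study-type fluid. This stands in part, so a reader should not infer that the data cannot answer the objective. What remains open is that no output makes the sum, that the crossover definition does not say whether permitted crystalloid maintenance in the albumin arm is crossover, and that non-study fluid has no volume.

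A reader might also infer that 4.6(b) will model randomised fluid and that the modelled difference would mostly reflect labelling. The documents do not support that. The wording in 4.6(b) is closer to the objective than to the endpoint; the fair criticism is that the variable is undefined. For 0-6 hours the labelling share is a minority of the apparent difference at the weights checked. The 750 mL ceiling also needs maintenance from randomisation onward, whereas Protocol 6.3 places it after resuscitation is complete. SAP 4.3 lists maintenance apart from resuscitation, which makes a resuscitation-only definition plausible.

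Two further points stand. Randomised-fluid volume is a legitimate delivery measure. And this is one secondary endpoint in a feasibility trial whose tests are to be read descriptively.

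**Conclusion.** The concern holds in a limited form. The objective asks for total IV fluid, the paired endpoint counts randomised fluid, and no listed output closes the gap.

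After hour 6 the between-arm comparison is not like with like wherever balanced crystalloid is given. Its size is 0 to 2,250 mL per patient on an assumed 0 to 125 mL/h for 18 hours with maintenance counted, and smaller if only resuscitation fluid counts or if later fluid is non-balanced.

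Within 0-6 hours the inequality is at most 750 mL, and it exists only if randomised fluid includes maintenance. To call the whole comparison distorted by construction would go too far, because that turns on an undefined term and on fluid use after 6 hours that the documents do not report. The change should be made, but it does not bear on the primary outcomes.

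**What to change.** In SAP 4.6 row 3, add each patient's total IV fluid (all recorded products, resuscitation and maintenance) for 0-6 and 0-24 hours, summarised by arm. Name that quantity as the volume variable in the 4.6(b) mixed linear model. Keep randomised-fluid volume as a descriptive delivery measure, and state whether it includes maintenance. State also whether permitted crystalloid maintenance in the albumin arm counts as crossover, so that components are neither missed nor counted twice.

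The cost is a little extra analysis work and a short SAP edit. The limit is data capture. Protocol 8.1 promises timing and volume of fluids only as detail on the trial intervention, and the SAP abstract describes recruitment as complete, so the total can cover only what was recorded. Check the eCRF first. Where it does not hold volumes of non-study fluid to 24 hours, report allocated plus crossover volume and state the uncaptured fluid as a limitation.

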## 4.7 Safety

Summary tables of adverse events, by treatment group and overall. Number of events and number of patients who had an event, showing all adverse events, serious adverse events, and non-serious adverse events. Tables will also be presented, stratifying events by MedDRA code; severity; relatedness; expectedness; and outcome.

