### 11.2 IDENTIFYING AEs AND SAEs

Participants will be asked about the occurrence of AEs/SAEs during the study and the medical records will be reviewed to identify these. AEs and SAEs will only be recorded and reported from consent until 7 days after randomisation due to the well-known safety profiles of the interventions. Open-ended and non-leading verbal questioning of

the participant will be used to enquire about AE/SAE occurrence. Participants will also be asked if they have been admitted to hospital, had any accidents, used any new medicines or changed concomitant medication regimens. If there is any doubt as to whether a clinical observation is an AE, the event will be recorded.

AEs and SAEs may also be identified via information from support departments e.g. laboratories.

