### **11.3 RECORDING AEs AND SAEs**

When an AE/SAE occurs, it is the responsibility of the Investigator, or another suitably qualified physician in the research team who is delegated to record and report AEs/SAEs, to review all documentation (e.g. hospital notes, laboratory and diagnostic reports) related to the event. The Investigator will then record all relevant information in the eCRF/AE log and on the SAE form (if the AE meets the criteria of serious).

Information to be collected includes dose, type of event, onset date, Investigator assessment of severity and causality, date of resolution as well as treatment required, investigations needed and outcome.

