### 11.5 RECORDING OF AEs

All adverse events identified between consent and 7 days after randomisation for each participant will be recorded in the medical notes for each participant. Only those events which would meet the criteria of seriousness and also qualify for reporting to the sponsor (see section 11.6.2) will be recorded on AE logs/ SAE forms and will be assigned the appropriate MedDRA Systems Organ Class (SOC) code.

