### **11.6.2 Reporting of SAEs/SARs/SUSARs and exemptions**

All SAEs that meet the definition given in section 11.1 and occur between consent and 7 days afterwards should be reported to the Sponsor unless they meet the exemption criteria below. These are outcome events are anticipated to occur in this participant group and will be exempt from reporting to the Sponsor:

Death related to infection (including multi-organ failure)

Critical care (HDU/ICU) admission

Acute kidney injury

Pulmonary oedema,

Allergy or anaphylaxis

Events That Are Common in the Trial Population:

The primary event of infection is classified as a pre-existing condition. As such, the occurrence or expected progression of infection or sepsis-related events including death will occur. In addition, participants are likely to have many minor adverse events during the course of the trial. These events will be recorded in the medical records and assessed in the same way as AE/SAEs. However, they are not usually recorded as AEs/SAEs, unless they are thought to be related to participant involvement in the trial.

Abdominal pain, nonspecific or related to a pre-existing condition

Accidents (domestic, traffic, occupational) including falls

Agitation or Anxiety

Atrial fibrillation or another cardiac dysrhythmia

Bleeding

Blood result abnormality (outside lab reported normal range) requiring no clinical intervention

Breathlessness related to a pre-existing condition e.g. COPD

Chest pain, non-specific or related to a pre-existing condition

Confusion or delirium

Constipation

Deep vein thrombosis/venous thromboembolism

Diarrhoea and/or vomiting

Dizziness or light headedness including vertigo

Dysphagia

Embolism

Fatigue, tiredness or sleepiness (somnolence)

Gastrointestinal disturbance, non-specific

Headache

Hypotension (if related to infection)

Hypoxia (if related to infection)

Incontinence, urinary or faecal

Malignancy, new diagnosis or new treatment for existing diagnosis

Mild ankle swelling not requiring treatment

Mood disorders

Muscle twitching

Any musculoskeletal condition e.g. arthritis or mechanical back pain

Peripheral vascular disease

Pneumothorax

Pressure sores or skin ulceration

Procedures occurring as part of the management of infection e.g. urinary catheter, central venous line, arterial line, intubation

Seizure

Sinus tachycardia (if related to infection)

Visual Loss e.g. cataract or macular degeneration or retinal detachment

Weight loss

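### SAP 4.7 tabulates all and non-serious adverse events, but Protocol 11.5 logs only serious, sponsor-reportable ones, and the protocol's own recording rules conflict

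*SAP*

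**What the plan says.** SAP 4.7 asks for numbers of events and of patients with an event, by treatment group and overall, "showing all adverse events, serious adverse events, and non-serious adverse events". It adds tables "stratifying events by MedDRA code; severity; relatedness; expectedness; and outcome". SAP 4.9 adds a listing of adverse events.

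On what is captured, Protocol 11.5 gives two tiers. First, "All adverse events identified between consent and 7 days after randomisation for each participant will be recorded in the medical notes". Second, "Only those events which would meet the criteria of seriousness and also qualify for reporting to the sponsor" go on to AE logs or SAE forms and receive a MedDRA code.

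Protocol 11.6.2 then narrows the reportable set. Infection-related death, critical care admission, acute kidney injury, pulmonary oedema, and allergy or anaphylaxis "will be exempt from reporting to the Sponsor". A long list of common events, including bleeding, venous thromboembolism, dysrhythmia, seizure and pneumothorax, is not usually recorded as AEs or SAEs "unless they are thought to be related to participant involvement in the trial".

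Other protocol sections point the other way. Section 11.2 says: "If there is any doubt as to whether a clinical observation is an AE, the event will be recorded". Section 11.3 tells the investigator to "record all relevant information in the eCRF/AE log and on the SAE form (if the AE meets the criteria of serious". Section 11.4.4 asks for a severity grade for every AE on the eCRF/AE log or SAE form.

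SAP section 3 says that safety data are analysed first by treatment received, with an intention-to-treat summary in addition.

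**The concern.** The SAP tabulates a class of event that the protocol's most specific recording rule keeps out of the trial log. A zero in the non-serious row would then mean that the events were not collected, yet nothing in SAP 4.7 tells a reader so. The serious row would look like a full count of serious harm but would hold only what remains after the exemptions. Deaths, for example, would appear there only when not attributed to infection.

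This trial is meant to inform a definitive study of a product that Protocol section 11 links, through its product information, to rare anaphylactic events. The safety table will be read on its own, so its title and rows should say what was captured.

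**Working it through.** No arithmetic applies. The check follows each class of event from its recording rule to the SAP table that would show it, taking Protocol 11.5 and 11.6.2 literally.

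| Event class | Reaches AE log or SAE form? | In SAP 4.7? | Elsewhere in the SAP? |
|---|---|---|---|
| Serious, not exempt, not on the common list | Yes, with MedDRA code | Yes | Listing, 4.9 |
| Non-serious | No, medical notes only | Row planned, no source | No |
| Infection-related death | No, exempt | No | Within all-cause death: 4.4 (30 days), 4.6 row 1 (in-hospital, 90 days) |
| Critical care admission | No, exempt | No | 4.6 row 5, modelled in 4.6(c) |
| Acute kidney injury, pulmonary oedema, allergy or anaphylaxis | No, exempt | No | 4.6 row 7 |
| Listed common event judged unrelated | Not usually | No | None, unless it leads to an outcome above |

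1. **Non-serious row.** Under 11.5 no non-serious event enters the log, so the row is empty by design.
2. **All-events row.** All events equal serious plus non-serious. With no logged non-serious events, this row repeats the serious row.
3. **Serious row.** It is populated but selective: it lacks the five exempt categories and the listed common events judged unrelated. Investigators make that relatedness judgement knowing the allocation, because the trial is open label (Protocol 5.5.3).
4. **If 11.2, 11.3 and 11.4.4 are followed instead.** Non-serious events do enter the log at those sites. With about 15 sites and no rule of precedence between the sections, the non-serious and all-events rows could mix sites that log everything with sites that log only reportable SAEs. Neither count would then be interpretable. The exception in 11.6.2 for trial-related common events could also let in a few non-serious events, which would be a selected subset.
5. **Grouping.** SAP 4.6 presents its table by randomised group and overall, and 4.4 falls under the intention-to-treat default. SAP section 3 puts treatment received first for safety data. SAP 4.3 expects crossover and tabulates it to 24 hours, so the two groupings can differ. The exempt harms never receive the grouping that section 3 puts first.
6. **Relatedness.** The common-event list has an exception for trial-related events. The exempt list, which includes allergy and anaphylaxis, has no such explicit exception. Read literally, the relatedness and expectedness tables in 4.7 would omit the one product risk that Protocol section 11 discusses by name.
7. **Time windows.** AEs run from consent to 7 days after randomisation (Protocol 11.2, 11.5). In the Protocol 7.1 schedule, kidney injury, pulmonary oedema and allergy are collected at discharge, mortality at discharge, Day 30 and Day 90, and HDU/ICU stay at discharge and Day 90. These cannot share a table titled to Day 7.

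**The case against.** The strongest reply is that the harms that matter most are already handled. Protocol 11.6.2 calls the exempt items outcome events, and the SAP routes them to 4.4 and 4.6; anaphylaxis also goes to the Data Monitoring Committee (Protocol section 11). This stands. A reader might infer that the safety table would be empty, or that the trial conceals its main harms. The documents support neither: non-exempt SAEs still fill 4.7, and every exempt category is covered by another planned table.

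A second reply is that SAP 4.7 fits Protocol 11.2, 11.3 and 11.4.4, and that Protocol 7.1 and 8.1 list adverse events as collected data. This also stands in part. The fault is as much an unreconciled protocol as a SAP error, and the non-serious row is empty only if 11.5 governs. It does not rescue the table, because the other outcome is a mixture of capture rules.

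A third reply is that SAP section 3 may mean only logged adverse events when it speaks of safety data, leaving 4.6 properly by randomised group. That reading is possible, but the SAP does not state it, and Protocol section 11 treats anaphylaxis as a safety matter.

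A reader might also try to count the events missing from 4.7 by applying the index-stay mortality of around 20% (Protocol 1.1) to 300 participants. That does not work. The figure covers a whole admission with a median stay of 10 days, while the AE window closes at Day 7. The documents give no seven-day mortality and no share of deaths due to infection, and all deaths enter the mortality analyses anyway.

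**Conclusion.** The point holds as a mismatch between the SAP and the protocol, together with a conflict inside the protocol. If 11.5 governs, one of the three planned rows is structurally empty, one is a duplicate, and the third is a selective count whose limits go unstated. If sites follow different sections, the first two rows cannot be interpreted. In addition, the exempt harms are not shown by treatment received, the grouping that SAP section 3 puts first for safety.

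No primary or secondary estimate changes and no exempt harm drops out of the analysis as a whole. The size is therefore that of a misleading table, not of a missing safety analysis. It should be corrected before reporting.

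The conclusion assumes that the eCRF, which is not among the documents, follows the protocol text. It also assumes that safety data in SAP section 3 includes the exempt harms; without that, the grouping point becomes a request for clarification and the rest stands.

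**What to change.** 1. **Protocol:** reconcile 11.2, 11.3 and 11.4.4 with 11.5, stating which events go on the eCRF/AE log and which stay in the medical notes.
2. **SAP 4.7, rows:** replace the all-events and non-serious rows with one table titled as sponsor-reportable serious adverse events, consent to Day 7. List the 11.6.2 exemptions beneath it, including the common events judged unrelated.
3. **SAP 4.7, footnote:** say that non-serious events were not systematically logged. Keep any that were logged in the 4.9 listing.
4. **SAP 4.7, harms:** cross-refer to 4.4 and 4.6. Show all-cause death, critical care admission, acute kidney injury, pulmonary oedema and allergy or anaphylaxis by treatment received as well as by randomised group, each labelled with its own collection window (discharge, Day 30 or Day 90). Use all-cause death, since Protocol 7.1 and 8.1 name no cause-of-death item.

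The outcome data are already collected, so the cost is wording plus a small amount of extra tabulation.
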